Changes from baseline to Week 4 and Week 8 in Schiff Sensitivity Score will be analysed using an analysis of covariance (ANCOVA) model. The model will include treatment as a factor and baseline Schiff Sensitivity Score as a covariate.

Changes from baseline in tactile score and VRS score will be analysed for weeks 4 and 8 separately using ANCOVA analysis with treatment and baseline Schiff stratification as factors and the corresponding baseline scores as a covariate in the model.

The adjusted mean for each treatment, and the differences between each pair of treatments together with their corresponding 95% confidence intervals and the p-values for treatment comparisons, will be provided.

Assumptions of normality and homogeneity of residuals will be evaluated and if serious departures are observed transformations will be investigated. If suitable transformations cannot be found, non-parametric tests such as Wilcoxon Rank Sum test or the van Elteren test will be used.

 GlaxoSmithKline	Document Name	207656 Clinical Protocol		
	Type	Version	Document Identifier	Effective Date
	eldo_clinical_doc	3.0; Most-Recent; Effective; CURRENT	090032d580d46916	25-May-2017 00:11:53
	Reason For Issue	Auto Issue		

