9.1 Sample Size Determination

A sufficient number of healthy subjects will be screened to randomise at least 100 subjects (approximately 50 to the experimental treatment, 25 to the negative control and 25 to placebo) to ensure 80 evaluable subjects complete the entire study. This will ensure approximately 40 evaluable subjects for the test treatment and 20 each for the negative control treatment and placebo.

 GlaxoSmithKline	Document Name	207656 Clinical Protocol		
	Type	Version	Document Identifier	Effective Date
	eldo_clinical_doc	3.0; Most-Recent; Effective; CURRENT	090032d580d46916	25-May-2017 00:11:53
	Reason For Issue	Auto Issue		

With this 40/20/20 distribution of the subjects in the treatment arms, the study has less than 50% power to detect a mean treatment difference of 0.36 in the Schiff sensitivity score using a two-sided t-test of significance level 0.05 for the experimental product against the negative control. The standard deviation used in this calculation is 0.8; this estimate is obtained from the GSKCH study 204763. When the experimental treatment group is compared with the combined group comprising of the negative control group and the placebo group using the two-sided t-test with the same estimates of mean difference, significance level and standard deviation, the study will have 51.1% power.

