9.3.4. Exploratory Analyses

Treatment comparisons other than the primary and secondary treatment comparisons mentioned above for the primary efficacy variable are exploratory. These will be performed in the similar way as the primary treatment comparison.

 GlaxoSmithKline	Document Name	207656 Clinical Protocol		
	Type	Version	Document Identifier	Effective Date
	eldo_clinical_doc	3.0; Most-Recent; Effective; CURRENT	090032d580d46916	25-May-2017 00:11:53
	Reason For Issue	Auto Issue		

The change from baseline to week 4 in the Schiff Sensitivity Score will be analysed using the same ANCOVA model as mentioned for the change from baseline to week 8 for this measure.

The change from baseline to week 4 in the tactile threshold will be analysed using the same ANCOVA model as mentioned for the change from baseline to week 8 for this measure.

Changes from baseline to weeks 4 and 8 in VRS will be analysed separately using the similar ANCOVA model as mentioned for the changes from baseline in tactile threshold.

Changes from baseline to weeks 4 and 8 in Schiff Sensitivity Score will further be analysed separately using the same ANCOVA model as mentioned above for this measure but by combining the marketed oral rinse group and the placebo group as one treatment group.

Similar analyses for the combined control group will also be done for the changes from baseline to weeks 4 and 8 for the tactile threshold and VRS using the same ANCOVA model mentioned above for the analysis of the secondary variable.

The adjusted mean for each treatment, and the difference between the pairs of treatments together with their corresponding 95% confidence intervals and the p-values for treatment comparisons, will be provided.

Assumptions of normality and homogeneity of residuals will be evaluated and if serious departures are observed, data transformations will be investigated. If suitable transformations cannot be found, non-parametric tests such as Wilcoxon Rank Sum test or the van Elteren test will be used.

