4.4.1.3 Supportive Analyses

The change from baseline in Schiff sensitivity score to post-treatment (Week 4 and 8) will be summarized and analyzed as detailed for the primary endpoint. Analysis assumptions will be investigated as detailed for the primary efficacy analysis.

The analysis will be conducted for:

- Test Product versus Placebo Product at Week 4 and 8
- Test Product versus Negative Control at Week 4

Similar analyses for a Combined Control group (Negative Control and Placebo) will also be performed for the changes from baseline in Schiff sensitivity score to Weeks 4 and 8 using the same ANCOVA model mentioned above for the analysis of the primary efficacy variable.

The adjusted mean for each treatment, and the difference between the pairs of treatments together with their corresponding 95% CIs and the P-values for treatment comparisons, will be provided (Table 14.2.1.1.2).

Test Product versus Combined Control group will be obtained by using contrast at Week 4 and 8. Below comparison will be tested:

- Test product versus Combined Control group at Week 4 and 8

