4.5 Analysis of Secondary Objectives

4.5.1 Efficacy (Secondary)

The change from baseline in tactile threshold at Week 8

The change from baseline in tactile threshold at Week 8 is the secondary efficacy endpoint.

The null hypothesis for the secondary endpoint is that the mean change from baseline in tactile threshold is equal between the two products.

$$H_0: \mu_1 = \mu_2$$

The alternative hypothesis is that the mean change from baseline in tactile threshold score is not equal between the two products.

$$H_1: \mu_1 \neq \mu_2$$

The primary treatment comparison of this secondary efficacy variable is:

Test Product versus Negative Product at Week 8.

All other treatment comparisons based on secondary efficacy variable are part of the exploratory objectives.

The subjects tactile threshold will be derived as the mean of the two test teeth at each visit assessed and the change from baseline will be derived from this mean tactile threshold. If tactile threshold for test teeth reported greater than 80g for post baseline assessment then in that case it will be consider as 90g.

Summary statistics of the observed mean tactile threshold scores and changes from baseline will be presented by treatment at Baseline, Week 4 and Week 8 (Table 14.2.2.1).

The change from baseline in tactile threshold at Week 8 will be calculated as the subject level mean change from baseline (on the two test teeth) and analyzed at Week 8 using ANCOVA with treatment and baseline Schiff stratification value as factors and baseline tactile threshold included as a covariate. Adjusted means of all treatments and their SEs, P-value and 95% CIs

will be presented. Treatment differences of all pairs of treatments will be provided together with P-values and 95% CIs (Table 14.2.2.2).

To visually inspect the treatment effect on tactile threshold scores, a plot across time, with the raw means together with SE bars will be produced. The plot will display a different symbol line for each treatment group (Figure 14.2.2).

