HISPANIC OR LATINO	xx (xx.x)	xx (xx.x)	...	xx (xx.x)
NOT HISPANIC OR LATINO	xx (xx.x)	xx (xx.x)	...	xx (xx.x)
AGE (YEARS)				
n	xx	xx	...	xx

1.5% w/w dipotassium oxalate monohydrate (KOX) and 0 ppm fluoride oral rinse

207656

Final Statistical Reporting and Analysis plan V1.0 5 Oct 2017

	Test Product (N=XX)	Negative Control (N=XX)	Placebo (N=XX)	Overall (N=XX)
MEAN	XX.X	XX.X	...	XX.X
SD	XX.XX	XX.XX	...	XX.XX
MEDIAN	XX.X	XX.X	...	XX.X
MINIMUM	XX	XX	...	XX
MAXIMUM	XX	XX	...	XX
STRATIFICATION				
MAXIMUM BASELINE SCHIFF SCORE 2				
	xx (xx.x)	xx (xx.x)	xx (xx.x)	xx (xx.x)
MAXIMUM BASELINE SCHIFF SCORE 3				
	xx (xx.x)	xx (xx.x)	xx (xx.x)	xx (xx.x)

Page x of y

PPD

1.5% w/w dipotassium oxalate monohydrate (KOX) and 0 ppm fluoride oral rinse

207656

Final Statistical Reporting and Analysis plan V1.0 5 Oct 2017

Protocol 207656

Program Run Date:xxxx

Table 14.2.1.1
Summary Statistics of Evaporative (Air) Schiff Sensitivity Score
Intent-to-Treat Population

Study Population: Intent to Treat (N=XXX)

Visit		Test Product (N=XX)		Negative Control (N=XX)		Placebo (N=XX)	
		Observed Value	Change from Baseline	Observed Value	Change from Baseline	Observed Value	Change from Baseline
BASELINE	N	XX		XX		XX	
	MEAN	X.XX		X.XX		X.XX	
	SD	X.XXX		X.XXX		X.XXX	
	MEDIAN	X.XX		X.XX		X.XX	
	MINIMUM	X.XX		X.XX		X.XX	
	MAXIMUM	X.XX		X.XX		X.XX	
WEEK 4	N	XX	XX	XX	XX	XX	XX
	MEAN	X.XX	X.XX	X.XX	X.XX	X.XX	X.XX
	SD	X.XXX	X.XXX	X.XXX	X.XXX	X.XXX	X.XXX
	MEDIAN	X.X	X.X	X.X	X.X	X.X	X.X
	MINIMUM	X.X	X.X	X.X	X.X	X.X	X.X
	MAXIMUM	X.X	X.X	X.X	X.X	X.X	X.X
WEEK 8	SAME AS ABOVE						

Page x of y

PPD

1.5% w/w dipotassium oxalate monohydrate (KOX) and 0 ppm fluoride oral rinse

207656

Final Statistical Reporting and Analysis plan V1.0 5 Oct 2017

Protocol 207656

Program Run Date:xxxx

Table 14.2.1.2
Statistical Analysis of Change from Baseline in Evaporative (Air) Schiff Sensitivity Score
Intent-to-Treat Population

Study Population: Intent to Treat (N=XXX)

	Test Product (N=XX)	Negative Control (N=XX)	Placebo (N=XX)
WEEK 4			
ADJUSTED MEAN [1]	XX.XX	XX.XX	XX.XX
SE [1]	XX.XXX	XX.XXX	XX.XXX
95% CI [1]	(XX.XXX, XX.XXX)	(XX.XXX, XX.XXX)	(XX.XXX, XX.XXX)
P-VALUE [1]	0.XXXX	0.XXXX	0.XXXX
COMPARISONS BETWEEN TREATMENTS			
	DIFFERENCE (SE) [1]	95% CI [1]	P-VALUE [1]
TEST PRODUCT VERSUS NEGATIVE CONTROL [1] *	XX.XX (XX.XXX)	(XX.XXX, XX.XXX)	0.XXX
TEST PRODUCT VERSUS PLACEBO [1]	XX.XX (XX.XXX)	(XX.XXX, XX.XXX)	0.XXX
TEST PRODUCT VERSUS COMBINED CONTROL [1,2]	XX.XX (XX.XXX)	(XX.XXX, XX.XXX)	0.XXX

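### Do the results tables need a negative control versus placebo row because the two controls are also pooled?

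*SAP*

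**What the plan says.** Protocol 9.1 expects 40, 20 and 20 evaluable subjects on test, negative control and placebo. For test versus negative control, the primary comparison, it states "less than 50% power to detect a mean treatment difference of 0.36 in the Schiff sensitivity score". For test versus the two controls together it gives a point value, 51.1%.

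Protocol 9.3.4 forms the pooled comparison "by combining the marketed oral rinse group and the placebo group as one treatment group". The SAP (4.4.1.3) instead keeps three arms in the model: "Test Product versus Combined Control group will be obtained by using contrast at Week 4 and 8".

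The documents differ on which differences will be reported:

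- **Protocol synopsis, Statistical Methods:** "the differences between each pair of treatments together with their corresponding 95% confidence intervals", which with three arms includes negative control versus placebo.
- **Protocol 9.3.2 and 9.3.3:** one pair only, the experimental against the marketed rinse. Section 9.3.4 speaks of pairs without listing them.
- **SAP 4.4.1.2 and 4.4.1.3 (Schiff):** a list in which every comparison involves the test product.
- **SAP 4.5.1 (tactile threshold):** "Treatment differences of all pairs of treatments will be provided together with P-values and 95% CIs". Section 4.6 says the same for VRS.
- **SAP Appendix 1, Table 14.2.1.2 shell:** test versus negative control, test versus placebo, and "TEST PRODUCT VERSUS COMBINED CONTROL [1,2". The programming notes adapt it for tactile threshold and VRS by changing footnote [1] only.

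SAP Section 5, which lists departures from the protocol, mentions only the per-protocol analysis.

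**The concern.** The two controls are different products: one is a marketed rinse with 0.02% sodium fluoride, the other a fluoride-free placebo. Averaging them gives a clean answer about the test rinse only if they behave alike. The natural check is the difference between them with an interval, and the shell has no line for it.

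The pooled comparison also carries the only point value for power, and that value assumes the same 0.36 advantage over both controls. If the controls differed, the contrast would estimate something between two different effects, and a reader of the comparison rows would see no direct measure of that. The study is method development prompted by mixed results in earlier rinse studies, so the behaviour of its controls is of interest. Built literally from the shell, the tactile and VRS tables would also fall short of SAP 4.5.1 and 4.6.

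**Working it through.** **Inputs.** Protocol 9.1: "two-sided t-test of significance level 0.05"; "The standard deviation used in this calculation is 0.8"; difference 0.36; 40/20/20 evaluable. The standard error of a difference is SD × √(1/n₁ + 1/n₂), and power comes from the non-central t distribution.

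**1. The plan's own figures.**
- Test versus combined control, 40 versus 40: SE = 0.8 × √(1/40 + 1/40) = 0.1789. Non-centrality = 0.36/0.1789 = 2.01 on 78 df. Power is 51.1%, as stated.
- Test versus negative control, 40 versus 20: SE = 0.8 × √(1/40 + 1/20) = 0.2191. Power is 36.6%, consistent with the stated bound.

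**2. Merged group or contrast.** Assume the contrast weights the controls equally (the SAP does not give the weights). Its SE is 0.8 × √(1/40 + ¼(1/20 + 1/20)) = 0.1789. At 20/20 this equals the merged-group value, so the change of method alters nothing in the planned precision.

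**3. How far the pooled power depends on the controls being alike.** Hold the advantage over negative control at 0.36 and vary the advantage over placebo. The varied values are assumptions, not figures from the documents.

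| Advantage over placebo | Contrast | Power |
|---|---|---|
| 0 | 0.18 | 16.9% |
| 0.16 | 0.26 | 30.0% |
| 0.36 | 0.36 | 51.1% |
| 0.56 | 0.46 | 71.9% |
| 0.72 | 0.54 | 84.6% |

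The dependence runs in both directions, and reporting one more row changes none of these figures.

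**4. What the extra row would show.** Negative control versus placebo, 20 versus 20: SE = 0.8 × √(2/20) = 0.253. The 95% half-width is 0.504 using the three-arm model's error (76 df) or 0.512 using the two arms alone (38 df). Power to detect a control difference of 0.36 is 28.4%, and 80% power needs a difference of about 0.73.

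**5. Whether the row is already recoverable.** Let a be test minus negative control, b test minus placebo, and c = (a + b)/2 the equal-weight contrast. The shell prints each with its SE.
- Negative control minus placebo is b − a.
- Var(c) = [Var(a) + Var(b) + 2Cov(a,b)]/4, so Var(b − a) = 2Var(a) + 2Var(b) − 4Var(c).
- With planning values, Var(a) = Var(b) = 0.2191² = 0.048 and Var(c) = 0.1789² = 0.032. Then Var(b − a) = 0.096 + 0.096 − 0.128 = 0.064, and √0.064 = 0.253, as in step 4.

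The identity holds in the covariate-adjusted model too, apart from rounding. It needs only that the three rows come from one fit and that the contrast is equally weighted. If the weights were unequal, the two adjusted means and their SEs, also in the shell, would give a close approximation.

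**The case for a change.** The best case for a change is that the row costs one line from a model already fitted, that the protocol synopsis and two SAP sections commit to it, and that SAP Section 5 does not declare its absence. Subjects are not blinded, and the Schiff score depends partly on their behaviour and verbal response, so the controls could differ through expectation as well as formulation. Protocol 9.2.4 also says the size of the difference matters more than significance, which favours showing intervals.

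The textual part of this stands. For tactile threshold and VRS, though, the SAP text itself calls for all pairs and names the tables. The only analysis shell shown is the Schiff one, and the reuse note deals with footnotes. An analyst working from the SAP would add the row there without an amendment. For Schiff, the SAP sections and the shell agree with each other, and only the synopsis sentence is broader. No objective in either document compares the two controls.

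The interpretive part is weaker. The controls are not simply treated as interchangeable: adjusted means, SEs and intervals are shown for each, test is compared with each separately, and raw summaries and plots are by arm. A marked divergence would be visible beside the pooled estimate.

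**Conclusion.** The inconsistency is real but minor, and no change to the plan follows. The primary result and every comparison named in the objectives are sound as planned. The pooled contrast is exploratory and is reported next to its two components.

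The missing Schiff row would carry an interval of about ±0.50 against a planning difference of 0.36. A non-significant result there would say nothing about the controls being alike, and only a gap of about 0.73 would be detected with 80% power. Its content is in any case implied by what the shell prints. Section 5's silence on the contrast is equally harmless, because both methods have an SE of 0.179 at 20 per control arm.

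These figures rest on the protocol's SD of 0.8, on 40/20/20 evaluable subjects and on equal contrast weights. They apply to the Schiff score; the documents give no SD for tactile threshold or VRS.
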